5.4.1.3 Lab Values Below the Lower Limit of Quantification

If the numeric value of a laboratory test (excluding PK analyses) is not available because it is below the lower limit of quantification (LLOQ), a logical value of < LLOQ should be used whenever applicable. In cases where a numeric value is required, eg, calculating the mean, the LLOQ will be used.

5.4.2 Definition of Baseline Values

Unless otherwise specified, the baseline value is defined as the value collected at the time closest to, but prior to, the start of study drug administration. If a patient is not dosed, the date of randomization will be used.

In the case that laboratory values from both the central lab and local lab are available before randomization, the most recent value from the central lab will be used as baseline, even if the sample date of the central lab result is prior to that of any local lab value.

5.4.3 Windowing of Visits

All data will be categorized based on the scheduled visit at which it was collected. These visit designators are predefined values that appear as part of the visit tab in the eCRF.

5.4.4 Justification of Pooling

All data from all sites will be pooled. Study center or treatment-by-center interaction will not be included in any statistical analysis.

5.4.5 Withdrawals, Dropouts, Lost to Follow-up

No patients will be replaced in this study.

5.5 Patient Disposition

A disposition of patients includes the number and percentage of patients for the following categories: patients in each of the study population, primary reason to discontinue from the treatment, patients discontinued from the study, and primary reason to discontinue from the study. All percentages will be based on the number of patients in the ITT population.

A listing will present data concerning patient disposition.

5.6 Demographics and Baseline Disease Characteristics

5.6.1 Demographics

Demographic and baseline characteristics will be summarized, including gender, age, race, weight, height, BSA, primary diagnosis, and other parameters as appropriate. No inferential statistics will be carried out.

The formulation for BSA is:

$BSA = \sqrt{\text{height}(\text{cm}) \times \text{weight}(\text{kg}) / 3600}$.

5.6.2 Medical History

Medical history will be listed for all patients.

5.6.3 Baseline Disease Status

Baseline disease status will be summarized by the treatment groups, including disease primary diagnosis, time since initial diagnosis (months), IPFP risk factors, Ann Arbor stage, and baseline Eastern Cooperative Oncology Group (ECOG) performance status.

Patient distribution by stratification factors will also be summarized.

5.7 Treatments and Medications

5.7.1 Concomitant Medications

Concomitant medications will be coded by preferred term using the World Health Organization (WHO) Drug Dictionary. The number and percentage of patients taking concomitant medications will be tabulated.

Brentuximab vedotin (ADCETRIS™)
Statistical Analysis Plan, Study C25003

Concomitant procedures will not be coded, but will be presented in a data listing in the clinical study report (CSR).

5.7.2 Study Treatments

The study treatments for this study are A+AVD and ABVD. ABVD consists of doxorubicin 25 mg/m², bleomycin 10 units/m², vinblastine 6 mg/m², and dacarbazine (DTIC) 375 mg/m². A+AVD consists of doxorubicin 25 mg/m², vinblastine 6 mg/m², dacarbazine (DTIC) 375 mg/m², and brentuximab vedotin (ADCETRIS) 1.2 mg/kg. A+AVD and ABVD will be administered by IV infusion on Days 1 and 15 of each 28-day cycle, for a total of 6 cycles. Details of study treatments administration is described in the protocol.

5.7.2.1 Extent of Exposure

The exposure to each component of study treatments A+AVD and ABVD will be characterized by total amount of dose received (mg or units), total number of doses received, number of treatment cycles, numbers and percentages of patients by maximum number of treatment cycles completed(1, 2, ... , 6).

A treatment cycle is defined as a cycle in which the patient received any amount of study drug.

Relative dose intensity (%) is defined as: $100 \times (\text{total dose received})/(\text{total dose intended})$. Total dose intended is the summation of the intended doses in all treatment cycles. The intended dose in each cycle is determined by the dose level when the patient was randomized.

Dosing data will also be presented in a by-patient listing.

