## **Brentuximab vedotin (ADCETRIS®)**

### **Clinical Study Protocol C25003 Amendment 7, EudraCT: 2011-005450-60**

first be discussed with the CRO and/or the Millennium project clinician. The order of administration must not be changed for the 50-patient subset in each treatment arm from whom additional PK samples are obtained (see Section 7.4.19).

Brentuximab vedotin is to be administered after AVD:

- **A:** brentuximab vedotin (ADCETRIS): 1.2 mg/kg will be administered by IV infusion over approximately 30 minutes on Days 1 and 15 of each 28-day cycle; the infusion is to start approximately 1 hour after the conclusion of the dacarbazine administration.

In the absence of infusion toxicities, the infusion rate for all patients must be calculated in order to achieve a 30-minute (approximate) brentuximab vedotin infusion period.

Brentuximab vedotin must not be administered as an IV push or bolus. It must be administered through a dedicated IV line and cannot be mixed with other medications.

The dose of brentuximab vedotin is 1.2 mg/kg. Dosing is based on patients' weight according to the institutional standard; however, doses will be adjusted for patients who experience a  $\geq 10\%$  change in weight from baseline. Actual weight will be used except for patients weighing greater than 100 kg; dose will be calculated based on 100 kg for these individuals. The dose will be rounded to the nearest whole number of milligrams.

Further brentuximab vedotin administration information can be found in the Pharmacy Binder.

No routine pre- or post-medications are required for A+AVD therapy.

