**Table 6-1 Recommended A+AVD Dose Modifications for Treatment-Associated Toxicity**

Toxicity	≤Grade 2		≥Grade 3	
Nonhematologic (excluding neuropathy)	Continue at same dose level.		Hold A+AVD dosing until toxicity has resolved to ≤Grade 2 or has returned to baseline. a	
Hematologic	Continue at same dose level.		For neutropenia, manage with growth factors (granulocyte colony stimulating factor [G-CSF] or granulocyte-macrophage colony stimulating factor [GM-CSF]) per institutional guidelines. For thrombocytopenia, consider platelet transfusion and/or proceed according to institutional guidelines. For anemia, manage per institutional guidelines.	
Peripheral neuropathy	Grade 1 Continue at same dose level.	Grade 2 Reduce dose to 0.9 mg/kg and resume treatment; if already at 0.9 mg/kg, continue dosing at that level.	Grade 3 Withhold brentuximab vedotin until toxicity is ≤Grade 2, then reduce dose to 0.9 mg/kg and resume treatment. If already at 0.9 mg/kg, consult with sponsor (AVD may be continued or held concurrently at physician's discretion.)	Grade 4 Discontinue brentuximab vedotin

a Patients who develop clinically insignificant Grade 3 or 4 electrolyte laboratory abnormalities may continue study treatment without interruption.

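### The SAP's relative dose intensity has no time term, and no other planned summary gives delay length or duration of exposure

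*SAP*

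**What the plan says.** SAP 5.7.2.1 (Extent of Exposure) builds the measure in four steps.

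- "Relative dose intensity (%) is defined as" 100 times total dose received divided by total dose intended.
- The denominator: "Total dose intended is the summation of the intended doses in all treatment cycles".
- Which cycles count: "A treatment cycle is defined as a cycle in which the patient received any amount of study drug".
- What is intended in each: "The intended dose in each cycle is determined by the dose level when the patient was randomized".

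The schedule is in SAP 5.7.2: "A+AVD and ABVD will be administered by IV infusion on Days 1 and 15 of each 28-day cycle, for a total of 6 cycles". That is 12 doses at 14-day spacing.

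For each component, SAP 5.7.2.1 also reports total dose, number of doses, number of cycles and the distribution of maximum cycles completed, and it promises a by-patient dosing listing. SAP 5.7.2.2 summarizes the action taken on each component in Cycles 1 to 6, and the time and type of any switch of frontline therapy.

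Protocol Table 6-1 provides for holds. For nonhematologic toxicity of Grade 3 or higher, neuropathy excluded, it says: "Hold A+AVD dosing until toxicity has resolved to ≤Grade 2 or has returned to baseline". It also has brentuximab vedotin withheld for Grade 3 neuropathy. Protocol 8.1.9 says that exposure will be tabulated, but the protocol gives no definition of dose intensity.

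**The concern.** Dose intensity normally means dose delivered per unit time relative to plan. The SAP quantity is a ratio of received to intended dose over the cycles a patient started. Two things follow. A hold has no effect on the ratio if the dose is later given. Cycles never started contribute nothing to the denominator.

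The arms share the AVD backbone and differ in brentuximab vedotin versus bleomycin. A reader of this open-label comparison will want to know whether ABVD was delivered close to plan, and whether added toxicity in the experimental arm slowed delivery of the backbone. The summary that carries the name dose intensity cannot answer the question about slowing in either arm, and nothing else planned answers it.

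**Working it through.** The documents state no value for this measure and no expected rate of delay, so there is no figure to reproduce. The definitions were applied to simple patterns; the delay lengths and stopping points are assumptions chosen for illustration.

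**Inputs**
- 2 doses per cycle, 6 cycles, 28-day cycles (SAP 5.7.2): 12 doses in 24 weeks (168 days).
- Dose level for the reduction example: 1.2 mg/kg (Protocol 6.2), reduced to 0.9 mg/kg (a level named in Table 6-1).

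**Formulas**, in full-dose units
- A, the SAP ratio: 100 × doses received / (2 × cycles started).
- B, share of the planned course: 100 × doses received / 12.
- C, time-based: 100 × (doses received / actual days) / (12 / 168), with actual days running from first dose to last dose plus 14.

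Check on schedule: 11 intervals × 14 = 154 days, plus 14 = 168 days. A, B and C all equal 100%.

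| Pattern | A (SAP) | B | Actual days | C |
|---|---|---|---|---|
| 12 full doses, one 2-week delay | 100% | 100% | 168 + 14 = 182 | 168/182 = 92.3% |
| 12 full doses, three 1-week delays | 100% | 100% | 168 + 21 = 189 | 168/189 = 88.9% |
| 12 full doses, six 1-week delays | 100% | 100% | 168 + 42 = 210 | 168/210 = 80.0% |
| Stop after both doses of Cycle 1 | 2/2 = 100% | 2/12 = 16.7% | 28 | 100% |
| Stop after both doses of Cycle 2 | 4/4 = 100% | 4/12 = 33.3% | 56 | 100% |
| Stop after Cycle 3 Day 1 | 5/6 = 83.3% | 5/12 = 41.7% | 70 | 100% |
| Stop after Cycle 6 Day 1 | 11/12 = 91.7% | 11/12 = 91.7% | 154 | 100% |
| 0.9 mg/kg from Cycle 4, on time | 87.5% | 87.5% | 168 | 87.5% |

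The last row is (6 × 1.2 + 6 × 0.9) / (12 × 1.2) = 12.6 / 14.4.

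The table shows three things.
- A does not respond to delay in any of the delay rows.
- A exceeds the share of the planned course whenever whole cycles are not started, and it is exactly 100% only when both doses of the last started cycle were given in full.
- C shows delay but not early stopping, so C cannot replace B.

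**Component counting.** The definition of a treatment cycle refers to study drug without naming a component. If brentuximab vedotin stops after Cycle 4 and AVD continues through Cycle 6, its ratio is 8/8 = 100% when cycles are counted on that agent, or 8/12 = 66.7% when they are counted on the regimen. The same choice arises for bleomycin, whose discontinuation for pulmonary toxicity is foreseen in footnote a of SAP Table 5-1.

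**The case against.** The best defence is that this is one descriptive line among several. Number of doses and maximum cycles completed reveal early stopping. So do time of switch (SAP 5.7.2.2), reasons for stopping treatment (SAP 5.5) and adverse events leading to discontinuation (SAP 5.11.1.4). Premature discontinuation of randomized treatment is also an event in EFS (SAP 5.8.4.4). Actions on each component by cycle, and adverse events that caused dose modification (SAP 5.11.1.1), may show that delays occurred. A ratio over started cycles answers a legitimate question, while a 12-dose denominator mixes tolerability with progression, death and the permitted switch after the Cycle 2 PET.

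Most of this stands. It defeats the inference that early stopping is concealed. It does not supply the length of a delay: an action recorded by cycle is not a duration, and no table gives weeks on treatment or dose per week. The by-patient listing is not a comparison between arms.

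A reader might infer two further things that the documents do not support.

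- *That the ratio would sit near 100% whatever happens.* Because the intended dose stays at the randomized level, reductions lower it, as do doses omitted within a started cycle.
- *That a correctly dosed heavy patient would look under-dosed.* At 120 kg, intended dose would be 144 mg instead of 120 mg (120/144 = 83.3%) only if the programmer disregarded Protocol 6.2, which says: "Actual weight will be used except for patients weighing greater than 100 kg; dose will be calculated based on 100 kg for these individuals". The SAP refers to the protocol for administration details, so leaving the cap unrepeated is not an error.

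The component question is an ambiguity, not a demonstrated mistake. The sentence listing measures by component does not itself name relative dose intensity, and the number of doses by component would reveal a dropped agent under either reading.

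**Conclusion.** The concern holds as a reporting defect. The measure is misnamed. It cannot register a hold followed by a full dose, and no other planned summary gives delay length or duration of exposure. In the illustrations it reads 100% where the time-based value is 92.3%, 88.9% or 80.0%. For early stopping it overstates the share of the planned course (100% against 33.3% after Cycle 2; 83.3% against 41.7% after Cycle 3 Day 1), but other planned tables show that stopping occurred.

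The actual effect depends on how often doses are delayed, which the documents do not say. What suffers is the descriptive comparison of delivered dose between the arms. The measure enters no test or decision rule, so a reader should not infer any effect on the mPFS analysis or the OS analyses.

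**What to change.** In SAP 5.7.2.1:

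1. For each component, define relative dose intensity as 100 × (dose received / actual weeks on treatment) / (planned dose / planned weeks). Actual duration runs from first dose to last dose plus 14 days. State whether those dates belong to the regimen or to the component; using the regimen's dates for every component keeps one clock and is consistent with item 3.
2. Report duration of exposure by arm.
3. Keep the present ratio under a different name, such as percent of intended dose in started cycles. State that cycles are counted on the regimen, so that a dropped component lowers its own ratio.
4. Add percent of the planned 12-dose total, because the time-based measure alone does not show early stopping.

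The cost is a few sentences and a little programming, assuming that the dosing data the SAP already plans to list include dates. Reported values will be less favourable wherever doses were delayed or courses cut short. No dosing rule, endpoint or test changes.

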5.7.2.2 Treatment Modifications

Action on each component of study treatments A+AVD and ABVD will be summarized by Cycles 1 through 6.

Patients who switch to another frontline therapy before completing A+AVD and ABVD will be summarized by time of switch and by treatment to which they switch.

5.8 Efficacy Analyses

All efficacy evaluations will be conducted using the ITT population unless otherwise specified.

5.8.1 Primary Efficacy Endpoint

The primary endpoint is mPFS (modified progression-free survival) per IRF assessment using the Revised Response Criteria for Malignant Lymphoma.

5.8.1.1 Definition

mPFS is defined as:

The time from the date of randomization to the date of the first of (1) documentation of progressive disease (PD); (2) death due to any cause; (3) for patients who are confirmed non-complete responders per IRF, receipt of anticancer chemotherapy or radiotherapy for HL after completion of frontline therapy, as defined in [Table 5-1](#); these patients' mPFS event date will be the date of the first PET scan post completion of frontline therapy demonstrating the absence of a CR, defined as a Deauville score of ≥ 3 .

Table 5-1 Completion of Frontline Therapy

Treatment History	Completion of Frontline Therapy
Did not switch therapy	Upon receipt of planned study drug regimen with no more than 2 missed doses of A+AVD or ABVD ^a
Switched therapy before completion of A+AVD or ABVD	Upon conclusion of 1 alternative anticancer regimen ^b for HL subsequent to A+AVD or ABVD discontinuation

a A "missed dose" refers to administration of the full study regimen of either A+AVD or ABVD. Patients may miss individual agents within the A+AVD or ABVD regimen (such as patients who discontinue bleomycin for pulmonary toxicity) without this counting as a missed dose.

b Receipt of chemotherapy OR radiation.

5.8.1.2 Handling of Missing Assessment and Censoring for mPFS Primary Analysis

The determination of the date of progression by the IRF will be used for the primary analysis. Sensitivity analyses will also be performed to evaluate the robustness of results.

For the mPFS primary analysis, disease assessment data should be collected according to the intended schedule of assessment, and the date of progression should be assigned based on the time of the first evidence of disease progression regardless of violations and

Brentuximab vedotin (ADCETRIS™)
Statistical Analysis Plan, Study C25003

discontinuation of study drug. For those patients who receive new anticancer chemotherapy or radiotherapy for HL after completion of frontline therapy without confirmed noncomplete-response, mPFS will be determined by PD or death. Detailed handling rules for missing assessments and censoring for the analysis of mPFS are presented in [Table 5-2](#).

Table 5-2 Handling of Missing Assessments and Censoring for mPFS Primary Analysis

Situation	Date of Progression or Censoring	Outcome
No baseline and/or no postbaseline assessment, no subsequent anticancer therapy after frontline therapy, no death	Date of Randomization	Censored
Disease progression documented between scheduled visits	Date of next scheduled visit	Progressed
No documented mPFS event	Date of last adequate assessment ^a	Censored
Lost to follow-up, withdraw consent before any documented mPFS event	Date of last adequate assessment ^a	Censored
Treatment discontinuation for undocumented disease progression after the last adequate assessment	Date of last adequate assessment ^a	Censored
mPFS event after more than one missed visit	Date of last adequate assessment ^a	Censored

a Adequate assessment is defined as there is sufficient data to evaluate a patient’s disease status.

5.8.2 Primary Efficacy Analysis

Final analysis of mPFS will be performed when 260 mPFS events have been observed, which is estimated to occur by 24 months after the last patient is randomized.

Stratified log-rank testing will be used to compare mPFS between the 2 treatment arms as the primary analysis. The stratification factors include region and number of IPFP risk factors at baseline (Section 5.2). The hazard ratios along with the 95% confidence interval (CI; 2-sided) will be estimated using the stratified Cox model with treatment as the explanatory variable. The Kaplan-Meier (K-M) survival curves and survival probability at 2 and 3 years along with the 2-sided 95% CIs will also be provided for each treatment group.

In addition, a stratified Cox regression model will be used to further evaluate the treatment effects on mPFS after adjusting for some prognostic factors. Besides treatment and the stratification factors (Section 5.2), the following prognostic factors will be included in the model simultaneously: age, race (white, non-white), baseline ECOG score, baseline cancer

Brentuximab vedotin (ADCETRIS™)
Statistical Analysis Plan, Study C25003

stage, baseline B symptoms, and PET results from Cycle 2. Additional exploratory analyses may be performed if deemed necessary.

For patients with mPFS events, the reasons leading to the determination of mPFS will be tabulated. For patients without mPFS events, the main reason for censoring will also be tabulated.

The proportional hazard assumptions will be examined and sensitivity analysis may be conducted if appropriate.

5.8.2.1 mPFS Sensitivity Analyses

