**Brentuximab vedotin (ADCETRIS®)**

**Clinical Study Protocol C25003 Amendment 7, EudraCT: 2011-005450-60**

information and efficacy data (CR rate per IRF for the A+AVD arm at least 5% lower than that of the ABVD arm, with trends toward inferior A+AVD efficacy for mPFS and other efficacy parameters).

The final analysis of the mPFS primary endpoint will be conducted when 260 mPFS events occur, approximately 2 years after randomization of the last patient; an interim efficacy analysis of OS will also be conducted at that time. The final analysis of OS will be conducted when 112 deaths occur, approximately 4 years after randomization of the last patient.

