**Brentuximab vedotin (ADCETRIS®)****Clinical Study Protocol C25003 Amendment 7, EudraCT: 2011-005450-60**

performed every 3 months during the first year of posttreatment disease follow-up, then every 6 months until study closure (5 years after the last patient is enrolled). If, for any reason other than death or documented disease progression, a patient discontinues randomization therapy (A+AVD or ABVD) after Cycle 2 Day 25 but before completion of randomization therapy, every effort must be made to obtain PET and CT scans prior to initiation of subsequent therapy for HL. Responses and relapses will be assessed by an IRF. Evaluations will be performed until progressive disease (PD) is documented, receipt of second-line anticancer therapy for HL (including chemotherapy or radiation), death occurs, or the end of study. Patients will be followed for survival until death or for a minimum of 5 years after enrollment of the last patient.

Deauville scoring (see Section 15.6) per IRF will be used to evaluate the results of patients' Cycle 2 Day 25 PET/CT. Patients whose disease earns a Deauville score of 4 or less will continue study drug treatment according to their randomized arm (ABVD or A+AVD). Patients whose PET-positive disease earns a score of 5 may, at the investigator's discretion, receive an alternative regimen (physician's choice) for the remainder of planned frontline therapy. Patients with a Deauville score of 5 who, at investigator's discretion, are taken off study drug will be continue to be followed for response assessment; switching therapy prior to completion of frontline therapy will not be considered an mPFS progression event. Of further note, any switch in therapy prior to completion of frontline therapy will not be considered an mPFS event.

An interim futility analysis will be conducted when the first approximately 348 patients have completed the regimen to which they were randomized (ie, received the planned study drug regimen with no more than 2 missed doses of A+AVD or ABVD) or have discontinued treatment prior to completion. The final analysis of the mPFS primary endpoint will be conducted when 260 mPFS events occur; an interim analysis of OS will also be conducted at that time. The final analysis of OS will be conducted when 112 deaths occur, approximately 4 years after randomization of the last patient.

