### **8.1.6.2 Analyses of Secondary Efficacy Endpoints**

Overall survival is designated as a key secondary endpoint. It will be tested at 1-sided 0.025 level when the test of mPFS is statistically significant at the final analysis.

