#### **Overall Survival**

OS is defined as the time from the date of randomization to the date of death. Patients without documented death at the time of analysis will be censored at the date last known to be alive.

Two formal analyses will be performed for OS. An OS interim analysis will be performed at the time of the final mPFS analysis, and the final analysis of OS will be performed when 112 deaths have occurred, assuming 5-year OS rates for the A+AVD and ABVD arms are 91% and 88%, respectively (HR=0.75). Overall type I error will be controlled using the O'Brien-Fleming method with a Lan-DeMets alpha-spending function.

Stratified log-rank testing will be used to compare OS between the 2 treatment arms. The hazard ratios along with the 95% CIs will be estimated using a stratified Cox regression model. The Kaplan-Meier method will be used to estimate the distribution of the OS endpoint for each treatment. Median survival times (if estimable), along with the 2-sided 95% CIs will be presented. Analysis of OS will be performed based on the ITT population.

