3.2.2 Testing Process and Significance for Key Secondary Efficacy Endpoint

Key secondary endpoint will be tested at 1-sided, 0.025 level only when the test of the primary endpoint (mPFS) is statistically significant. If the test is statistically significant, we will conclude that the A+AVD treatment can make improvement in OS compared with the ABVD treatment.

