4. INTERIM ANALYSIS

4.1 Interim Analysis

There will be 2 formal interim analyses in this study.

The first formal interim analysis to be performed is a futility analysis. The CR rate at the end of frontline therapy will be analyzed when the first approximately 348 patients have completed the regimen to which they were randomized (ie, received the planned study drug regimen with no more than 2 missed doses of A+AVD or ABVD) or have discontinued treatment prior to completion. Recommendation by the independent data monitoring committee (IDMC) whether to terminate the study based on this interim analysis will be determined upon evaluation of the overall safety information and efficacy data, specifically if the CR rate per independent review facility (IRF) for the A+AVD arm is at least 5% lower than that of the ABVD arm and trends in mPFS and other efficacy endpoints suggest inferior efficacy in the A+AVD arm. This futility analysis does not require adjustment of the type I error.

The second formal interim analysis is for OS to be performed at the time of the final mPFS analysis. Overall type-I error for OS will be controlled using the O'Brien-Fleming method with a Lan-DeMets alpha spending function, with final OS analysis scheduled for when 112 deaths have occurred.

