5.1 Sample Size Justification

The primary endpoint of the study is mPFS, and the study is powered on the following assumption: a 2-year mPFS of 81% for patients in the A+AVD treatment group versus 73% for patients in the ABVD treatment group (HR = 0.67, assuming an emergent plateau in the PFS event rate after 2 years). A total of 260 mPFS events will provide 90% power to detect a hazard ratio of 0.67 at a 1-sided significance level of 0.025 using a log-rank test.

Approximately 1240 patients will be randomized to achieve (with 95% probability) 260 mPFS events in about 60 months assuming 36 months of accrual, a 5% annual dropout rate, and 24 months of mPFS follow-up after last patient in.

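### Does the final mPFS analysis need a fallback rule in case 260 events are never reached?

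*SAP*

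**What the plan says.** All three places that time the final mPFS analysis use the event count. SAP 5.8.2 has "Final analysis of mPFS will be performed when 260 mPFS events have been observed, which is estimated to occur by 24 months" after the last randomization. Protocol 4.1 has "The final analysis of the mPFS primary endpoint will be conducted when 260 mPFS events occur; an interim analysis of OS" at the same time, and the Protocol Summary has "conducted when 260 mPFS events occur, approximately 2 years after randomization of the last patient". The dates are projections, not cut-offs.

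Two OS steps depend on this analysis:
- **OS interim.** Protocol 8.1.6.2 says "An OS interim analysis will be performed at the time of the final mPFS analysis", and SAP 4.1 agrees: "The second formal interim analysis is for OS to be performed at the time of the final mPFS analysis".
- **OS gate.** Protocol 8.1.6.2 says of OS: "It will be tested at 1-sided 0.025 level when the test of mPFS is statistically significant at the final analysis". SAP 3.2.2 says "Key secondary endpoint will be tested at 1-sided, 0.025 level only when the test of the primary endpoint (mPFS) is statistically significant".

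The final OS analysis has its own trigger, 112 deaths, expected about 4 years after the last randomization.

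Protocol 8.1.1 and SAP 5.1 assume 2-year mPFS of 81% versus 73%, 36 months of accrual, 5% annual dropout and 1240 patients, giving 260 events with 95% probability in about 60 months. For the period after 2 years the protocol assumes a lower event rate and the SAP writes "assuming an emergent plateau in the PFS event rate after 2 years". Neither document puts a number on it.

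**The concern.** A pure event trigger works while events keep arriving. In a disease that many patients are cured of, they may nearly stop. If the count stalled below 260, a literal reading would start neither the mPFS test nor the OS interim, and 112 deaths could be reached with the OS gate still untested. Someone would then have to choose a data cut-off after learning of the shortfall, in an open-label trial, which invites questions about the timing. The Amendment 7 rationale shows that the sponsor saw the risk, since the enrolment increase was made to raise the chance of observing 260 events.

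**Working it through.** **1. The plan's event number.** Inputs (SAP 5.1): HR 0.67, one-sided 0.025, 90% power, 1:1 allocation. Schoenfeld events = 4(1.960 + 1.282)² / (ln 0.67)² = 262.06, or 263 when rounded up, close to 260. Power at D events = Φ(√D/2 × |ln 0.67| − 1.960):

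| Events | Power |
|---|---|
| 260 | Φ(3.229 − 1.960) = 89.8% |
| 250 | Φ(3.166 − 1.960) = 88.6% |
| 240 | Φ(3.102 − 1.960) = 87.3% |

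**2. Expected events if nothing happens after 2 years.** I assume a constant hazard up to 2 years, uniform accrual, exponential dropout and 620 patients per arm. Annual hazards are −ln(0.81)/2 = 0.1054 and −ln(0.73)/2 = 0.1574. Dropout is d = −ln(0.95) = 0.0513. With a flat plateau the probability of an observed event is h/(h + d) × (1 − exp(−2(h + d))):
- A+AVD: 0.1054/0.1567 × (1 − e^−0.3133) = 0.1809
- ABVD: 0.1574/0.2086 × (1 − e^−0.4173) = 0.2573

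Expected events = 620 × (0.1809 + 0.2573) = 271.7. Even in this limiting case 260 is the likely outcome. Summing the two binomial distributions exactly gives P(at least 260) = 80%. Longer follow-up cannot raise this, because every patient still in follow-up has passed 2 years.

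**3. Events that continue at a reduced rate.** Let the hazard after 2 years be a fraction r of the earlier one. The documents give no value for r, so a range is shown.

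| 2-year mPFS | r | 24 months after last patient | 36 months | 48 months |
|---|---|---|---|---|
| 81%/73% (plan) | 0 | 80% | 80% | 80% |
| 81%/73% | 5% | 92% | 96% | 98% |
| 81%/73% | 7.5% | 95.0% | 98.4% | 99.5% |
| 81%/73% | 10% | 97% | 99.5% | 99.9% |
| 80%/72% (assumed) | 0 | 95% | 95% | 95% |
| 80%/72% | 7.5% | 99.3% | 99.9% | >99.9% |
| 82%/74% (assumed) | 0 | 51% | 51% | 51% |
| 82%/74% | 7.5% | 79% | 90% | 96% |

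The plan's 95% corresponds to r of about 7.5%. A one-point error in the 2-year rates matters in both directions.

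**4. The cost of a shortfall.** At 81%/73% and r = 0, the 20% of trials that fall short have a mean of 251.5 events and 88.8% power. Only 1.2% of all trials end below 240. Power averaged over all trials, with events capped at 260, is 89.6% against 89.8%.

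**5. Error control.** mPFS is tested once at one-sided 0.025. Protocol 6.7 and SAP 5.3 keep aggregate efficacy data from the study team, the investigators and the patients, and the independent review facility is blinded to treatment. A cut-off chosen on the pooled count carries no information about the comparison between arms, so it does not inflate the type I error. The OS gate read literally is conservative: without a significant mPFS test, no OS claim is possible.

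**The case for a change.** The best argument for a change is that a sentence costs little and settles the matter before anyone knows the count. By the plan's own figure, about one trial in twenty is short at 60 months. The SAP speaks of a plateau and plans a cure model (SAP 5.8.2.2), so waiting may not help. At an assumed 82%/74% with r = 7.5%, the shortfall risk at 24 months is 21%. The projection also leaves out the SAP Table 5-2 rule that censors events after more than one missed visit, which would lower the count. The documents also do not agree on when follow-up ends: about 4 years after the last randomization in Protocol 4.3, and 5 years in Protocol 4.1 and 7.10.

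The absence of a rule stands, and so do these sensitivities. Their weight is limited:
- The flat plateau is a bound. The protocol assumes a decrease rather than zero, and death from any cause is an mPFS event. If half of the 2-year events fell at month 7 (assumed, to mimic events dated at the scan after frontline therapy), the flat-plateau figure would rise from 80% to 84.5%.
- The 82%/74% rates have no source in the documents, and 80%/72% is no less plausible.
- Both follow-up horizons lie well beyond 24 months, so either leaves time to wait.
- A date that applies whichever condition comes first has its own cost. At 82%/74% and r = 7.5%, a 36-month limit (used only as an example) would stop 9.7% of trials early. More than half of these would have reached 260 by 48 months, since the share reaching it rises from 90.3% to 96.0%.

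**Conclusion.** No change is needed. The plan leaves a contingency unwritten, but no rule it states gives a wrong result. The main safeguard, a larger sample, is already in place. On the plan's own rates the shortfall risk is 5% at 24 months after the last patient, falling to 1.6% and 0.5% at 36 and 48 months if the later hazard is about 7.5% of the earlier one. It is 20% only if events stop altogether after 2 years. Final OS is expected at about 4 years, so reaching 112 deaths with mPFS still untested is a remote case.

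If the count did stall, the sensible course is plain: fix a cut-off on pooled events while blinded to aggregate efficacy data, test mPFS once at one-sided 0.025, then apply the OS gate. At 240 to 250 events that costs about 1 to 3 points of power. These sizes rest on a constant hazard up to 2 years, uniform accrual, exponential dropout and no loss of events to the missed-visit censoring rule.
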